4.5 Patient Renumeration

Patients do not receive economic compensation for trial participation.

5. Treatment Procedures and Interventions

5.1 Treatment Procedure

5.2.1 Treatment Area Demarcation

At baseline (Day 0), BCC delineation will be performed clinically and by D-OCT, RCM and HIFU imaging. The treatment area will include the delineated tumor and a 5 mm margin of surrounding skin. After delineation, treatment areas will be photographed and mapped on a transparent template to document baseline tumor size and location.

5.2.2 Ablative Fractional Laser (AFL):

Before AFL exposure, hairs will be shaved and treatment areas numbed with standard local analgesia (lidocaine HCL 1% +epinephrine 1:100.000 injection). Depending on tumor thickness, treatment areas will then be exposed to 1-2 stacked pulses of maximum 50 mJ/microbeam (mb) and up to 10 % density. Specific laser settings are established based on results from a currently ongoing clinical trial at Bispebjerg Hospital (EudraCT-nr 2017-002843-14).

5.2.3 Topical Cisplatin

After AFL exposure, a well consisting of a customized hydroactive bandage (DuoDerm Hydroactive™, ConvaTec, Flintshire, UK) is applied to the test area, defined as the BCC and 5 mm margin, and sealed shut with transparent dermatological film (TegaDerm® film dressing, 3M Medical, MN, USA). Cisplatin solution 0.1% (Accord Healthcare Limited A/S) is applied through the transparent film using a blunt-tipped syringe, ensuring spatial containment of the solution with no loss to the environment. The amount of solution will fill the well to ensure coverage of the entire skin surface. Accordingly, up to 0.25 ml per cm² (0.25 mg) will be applied depending on tumor delineation. Cisplatin is left on the skin for 60 minutes, whereafter the solution is removed by light suction using a blunt-tipped syringe. After drug removal, all materials will be disposed of according to guidelines for materials contaminated with cytotoxic-agents.

5.2.4 Topical 5-Fluorouracil (5-FU)

After cisplatin removal, the well bandage is disposed of and a thick amount of Efudix® 5% 5-FU cream (Meda Pharmaceuticals A/S, UK) is applied to the entire test area (corresponding to up to 0.125 ml per cm² skin). After 5-FU application, transparent dermatological film (TegaDerm® film dressing, 3M Medical, MN, USA) is applied to the test area as an occlusive dressing. The cream is left on the skin until next control visit. Thus, on Day 1 and 5, Efudix cream is reapplied at the same dose. The cream is removed on Day 7 after AFL treatment.

STUDY SET UP	Visit 1 Screening	Visit 2 Treatment Day 0	Visit 3 Day 1	Visit 4 Day 5 +/- 2 days	Visit 5 Day 14 +/- 3 days	Visit 6 Treatment* Day 30 +/- 5 days	Visit 7 Month 3 +/- 5 days
Screening & enrolment							
Informed consent	✓						
Inclusion/exclusion criteria	✓						
Relevant medical history	✓						
Location of BCC	✓						
Pregnancy test when relevant		✓				✓	
Interventions							
AFL		✓				(✓)	
Apply topical cisplatin(60min)		✓				(✓)	
Apply 5-FU under occlusion		✓	✓	✓		(✓)	
Clinical LSR evaluation							
FDA-approved LSR scale		✓	✓	✓	✓	✓	
Clinical photos		✓	✓	✓	✓	✓	
Safety							
Clinical evaluation		✓	✓	✓	✓	✓	
Tumor size and clearance evaluation							
Clinical/dermoscopic photos		✓	✓	✓	✓	✓	
D-OCT		✓				(✓)	
RCM		✓					
HIFU		✓				(✓)	
Biopsy							✓

*Offered if BCC residual or recurrence; (✓): Treatment/technique can be relevantly applied if tumor residuals are identified clinically or by D-OCT/RCM and there is no crusting etc. LSR: Local skin reactions, RCM: Reflectance confocal microscopy, D-OCT: Dynamic optical coherence tomography

5.2 Intervention Details

- **Ablative Fractional Laser (AFL):** Laser irradiation will be performed using the UltraPulse® laser system with DeepFx handpiece (Lumenis, Santa Clara, USA) which is a 10,600 nm CO₂ laser CE-marked for dermatological use. The procedure is expected to take 15 min.
- **Cisplatin Solution:** The topically-applied cisplatin solution (Accord Healthcare Limited A/S) is approved for commercial use and is administered intravenously at significantly higher doses in the conventional oncological setting. The drug will be provided by the department of Dermatology at Bispebjerg Hospital. 1 ml contains 1 mg cisplatin (0.1%). Other ingredients are sodium chloride and sterile water. For the study, the drug will be supplied in labelled, 3 ml blunt tipped syringes (preprepared by the hospital pharmacy pending a

contractual agreement) and will be light protected and stored at room temperature. The solution will in this study be applied topically for 60 min.

- **Efudix® 5-FU Cream:** The cream (Meda Pharmaceuticals A/S, UK) is used commercially for topical use where standard regimens for BCC consist of twice daily application for 4-6 weeks. The cream sold under special license and is provided via the department of Dermatology at Bispebjerg Hospital. The drug is packaged in tubes of 20 grams and stored at 5 degrees. 1 mg contains 50 mg 5-FU (5%). Other ingredients are stearyl alcohol, vaseline, polysorbate 60, propylene glycol, methyl parahydroxybenzoate, propyl-parahydroxybenzoate and purified water. Topical application under occlusion for up to 7 days will be used on treated area.

5.3 Supplementary treatment

Management of pain will be 1 g paracetamol or 200 mg ibuprofen. No rescue medicine is necessary.

5.4 Compliance

All treatments are performed at the dermatological department, Bispeberg Hospital reducing the need for compliance-ensuring efforts. Securing adequate 5-FU occlusion will occur on control visits.

6. Outcome Measures & Methods

Outcome measures are evaluated in a non-blinded manner by physicians at the department of dermatology, Bispebjerg Hospital.

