3.2 Randomization and Blinding

Due to the uncontrolled open-label study design, no randomization/blinding is planned.

*Phase IIa trial: Small preliminary clinical trials to evaluate safety and/or efficacy in selected populations of patients with the disease or condition to be treated, diagnosed, or prevented. Objectives may focus on dose-response, type of patient, frequency of dosing, or numerous other characteristics of safety and efficacy.

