6.2 Secondary Outcome

Tumor Response measured as:

- I) Tumor size (mm) and clearance (yes or no) will be evaluated clinically and using non-invasive D-OCT, HIFU and RCM imaging at baseline, Day 30 and Month 3 (Section 5, Appendix 1). If residual tumor is identified at 3 months follow-up, patients will receive conventional treatment according to national guidelines. Imaging techniques are described in section 6.3.
- II) Histological verification of tumor clearance will be performed 3 months after first treatment using tissue sections from a 4 mm punch biopsy. If residual tumor is identified at 3 months follow-up, patients will receive conventional treatment according to national guidelines.

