6.3 Methods for Outcome Assessment

6.3.1 Clinical Evaluation and Digital Photography

Clinical evaluation of LSRs (erythema, edema, flaking, crusting/scabbing and pustulation) in treated areas will be performed by a non-blinded physician using a FDA-approved LSR scale at Days 1, 5, 14 and 30 after baseline. The scale assesses severity of individual LSR parameters on a 0-4 points scale: none, mild, moderate, severe. Tumor size (mm) and clearance (yes or no) will also be evaluated by standard clinical dermoscopy at Day 30 and Month 3 (Appendix 1). Digital photography using a Canon Camera will be performed prior to, during, after treatment, and at control visits under standardized conditions. All images are assigned an ID-number and anonymized.

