6.3.2 Imaging

All imaging devices have the size of a modern ultrasonography system and handheld, flexible probe. All systems are CE-marked and FDA approved.

High Intensity Focused Ultrasound (HIFU)

HIFU will be performed at baseline, day 30 (if imaging is not obstructed by overlying skin reactions) and month 3 after treatment. A GE LOGIQ P9 unit (General Electric Medical Systems, known as GE Healthcare, Little Chalfont, Buckinghamshire, UK) with a high frequency probe 9 - 15 MHz will be used to identify tumors in skin. The system is CE marked to council directive 93/42/EEC on medical devices (FDA K152309) with a 50-200 μm resolution and a penetration depth of 0.75-2 cm. HIFU allows volumetric images of tumors in real-time, using 4D transducers. BCC tumors are characterized as well-defined, black, round to elongated areas often with distinct internal white dots. The HIFU modality is sensitive to the generally slower blood flow in skin. During imaging, standard imaging gel is placed on the skin in order to avoid skin compression under examination. The acquired images are saved in a digital archiving computer system for subsequent evaluation.

Dynamic Optical Coherence Tomography (D-OCT)

D-OCT will be applied at baseline to delineate horizontal and vertical BCC tumor margins and subsequently customize settings for relevant AFL channel dimensions. D-OCT will also be used to assess tumor size and clearance at control visits on Day 30 (if imaging is not obstructed by overlying skin reactions) and Month 3 after treatment (Section 5, Appendix 1). A commercially available, CE-marked (CE 545451, FDA K153283) OCT system (Vivosight[®] DX, Michelson Diagnostics Ltd., Kent, UK) with a laser wavelength of 1305 nm will be used.

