For the evaluation of D-OCT, RCM and HIFU images, qualitative and quantitative measurements will be obtained. Skin morphology in D-OCT and RCM images is evaluated using the integrated VivoSight° software for the OCT and the integrated VivaScan° software for the RCM VivaScope°. Furthermore, OCT, RCM and HIFU images will be analyzed using ImageJ software (Java-based freeware, National Institutes of Health, Maryland, USA).

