6.3.3 Histology

At the 3 month visit, a 4 mm punch biopsy will be taken centrally in treatment area for histological verification of tumor clearance. Biopsy tissue will undergo standard sectioning and histological evaluation by a board-certified pathologist at the Department of Pathology, Bispebjerg Hospital. If tumor residual/recurrence is confirmed, test areas will be treated according to clinical guidelines.

7. Potential Risks and Side Effects

In general, no serious or systemic side effects are assumed but will be reported to the relevant authorities if they occur. Topical 5-FU cream and AFL are used daily at Bispebjerg Hospital's dermatological clinic and are well-tolerated. Cisplatin has previously been examined in a live pig study where no systemic drug uptake or effects were observed. Any obtained information about adverse effects related to this study will be recorded systematically.

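### Stored tumor images are to be read without masking to visit, earlier scan or Month 3 histology, so reader expectation can enter the before/after tumor-response result

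*Combined protocol and SAP*

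**What the plan says.** Section 6 opens with a rule covering the outcome measures in general: "Outcome measures are evaluated in a non-blinded manner by physicians at the department of dermatology, Bispebjerg Hospital". The only reason given is in Section 3.2: "Due to the uncontrolled open-label study design, no randomization/blinding is planned".

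The outcome at issue is the secondary one. Section 6.2 states: "Tumor size (mm) and clearance (yes or no) will be evaluated clinically and using non-invasive D-OCT, HIFU and RCM imaging". The planned time points are baseline, Day 30 and Month 3, except that Appendix 1 leaves RCM out at Day 30.

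On handling of the images, the HIFU paragraph of Section 6.3.2 says: "The acquired images are saved in a digital archiving computer system for subsequent evaluation". The software paragraph of the same section says that "OCT, RCM and HIFU images will be analyzed using ImageJ software", in addition to the device software for OCT and RCM. Section 6.3.1, in its text on photography, says: "All images are assigned an ID-number and anonymized".

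Histology is handled separately. Under Section 6.3.3, "a 4 mm punch biopsy will be taken centrally in treatment area for histological verification of tumor clearance", followed by "histological evaluation by a board-certified pathologist at the Department of Pathology, Bispebjerg Hospital".

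**The concern.** Open-label treatment explains why nobody can be blinded to treatment, and why bedside grading of skin reactions is unblinded. It does not explain why someone measuring a stored image must know when it was taken, what the earlier scan showed, or what the biopsy found. In a before/after study that knowledge is the source of bias, because there is only one treatment.

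Tumor response is a change from the patient's own baseline. With no control arm, a tendency to trace smaller or call clear after treatment is not cancelled by the same tendency in a comparator. The direction of expectation is on record: Section 11 says the team expects treatment to succeed. Section 9.1 weighs tolerability against the efficacy observed, so the tumor result bears on the trial's main judgement although it is secondary.

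Imaging also covers tissue that the biopsy does not reach. If a doubtful image were settled with the biopsy report in hand, it would add little to that report.

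**Working it through.** The plan states no figure to reproduce: Section 9.1 says no formal calculation was done. The check is mainly of the text, with arithmetic for scale only.

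**1. Is masking of image readers set anywhere?**
- Section 3.2: no blinding, because of the design. It is silent on visit, earlier scan and histology.
- Section 6, opening: non-blinded evaluation, as a general rule.
- Sections 6.2 and 6.3.1: no reading order. The ID number and anonymization are stated under photography, and nothing says the visit is hidden.
- Section 6.3.2: no masking, no random order, and no requirement to finish image reads before pathology returns.

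So nothing prevents a Month 3 image being measured beside its baseline, or after the biopsy report.

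**2. Could a masked read be done?** Storage for later evaluation is explicit for HIFU only. For OCT and RCM it is an inference from the planned ImageJ and device-software analysis, which works on saved files. Some reads must be live: baseline delineation (Section 5.2.1), the Day 30 read behind the offer of repeat treatment (Section 3.3), and the Month 3 read, since residual tumor leads to conventional treatment (Section 6.2). A masked read would therefore be an additional one. The visit table, as reproduced, carries no Month 3 imaging mark. Sections 6.2 and 6.3.2 and Appendix 1 plan Month 3 imaging, and I follow those.

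**3. How much tissue does the biopsy leave to other methods?** Punch area = π × 2² = 12.6 mm². For an assumed round lesion of 10 mm diameter, lesion area = π × 5² = 78.5 mm², and the area with the 5 mm margin = π × 10² = 314.2 mm². The punch covers 12.6/78.5 = 16% of the lesion and 12.6/314.2 = 4% of the treated area. Section 4.2 admits lesions up to 20 mm (face, scalp) or 50 mm (elsewhere), for which the shares are smaller. Outside the punch, clearance rests on clinical, dermoscopic and imaging reads.

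**4. Scale of a changed reading.** Inputs: up to 12 lesions per subtype and 24 in all (Sections 4 and 9.1).
- One call changed: 1/12 = 8.3 points; 1/24 = 4.2 points.
- Assumed example: 9/12 = 75.0% (exact 95% interval 42.8 to 94.5) becomes 10/12 = 83.3% (51.6 to 97.9).
- If a share f of truly residual lesions is called clear and no clear lesion is called residual, apparent clearance = p + (1 − p) × f. With f assumed at 10% to 30%, a true 60% reads as 60 + 40 × 0.1 = 64% to 60 + 40 × 0.3 = 72%. A true 80% reads as 82% to 86%.

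The documents give neither p nor f.

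**The case against.** The strongest reply is that this is a disclosed choice. The trial is exploratory, single-arm and openly non-blinded, its primary outcome is tolerability, and Section 3.4 gives imaging a supporting role. No efficacy threshold is set that a shifted clearance rate could cross, and at 12 lesions per group sampling uncertainty is far larger than one changed call. All of this stands and limits the weight of the point. It does not remove it, because random error and an avoidable one-directional error are different things, and the second can be reduced here with existing staff.

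Three stronger readings are tempting, and the documents do not support them.
- A reader might infer that every outcome, histology included, is read unblinded. Section 6.3.3 gives histology to a pathologist outside dermatology, whose masking is simply not stated.
- A reader might infer that agreement between imaging and histology is inflated. Section 9.3 plans no agreement analysis. Month 3 imaging and biopsy also belong to the same visit, so a bedside call would ordinarily come before the pathology report. Only a later read could be influenced, and the plan neither schedules nor excludes one.
- A reader might put a number on the bias, for instance 4 doubtful scans of 24 all called clear when an even split was expected, a shift of 2/24 = 8.3 points. Nothing in the documents says how many scans would be doubtful or which way they would be called.

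It is also fair that masking would be imperfect. In at most 24 lesions the physicians may recognise their own cases. Every baseline lesion is verified BCC, so an image without tumor is almost certainly post-treatment. Up to 6 preliminary-study patients will have had a punch at 24 hours (Section 3.5). Masking therefore helps most with equivocal images and size tracings.

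**Conclusion.** The point holds for image-based tumor size and clearance: the plan makes outcome evaluation by dermatology physicians non-blinded and sets no masking of image readers to visit, earlier scan or Month 3 histology. With within-patient comparisons and no control arm, reader expectation can enter the secondary tumor-response result. Its size is not derivable from the documents; the figures above show only how sensitive small groups are to single calls. The conclusion assumes that D-OCT and RCM files, like HIFU images, are kept and can be read later. It does not extend to skin-reaction grading, side effects or histology. This is an inexpensive improvement worth making before image reading begins, not an error that invalidates the trial.

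**What to change.** Amend Section 6 as follows.
- Skin reactions, side effects and bedside assessments stay unblinded. The Month 3 clinical and dermoscopic clearance call is entered before the biopsy result is available.
- For the outcome analysis, stored D-OCT, RCM and HIFU files and dermoscopic photographs are re-coded and read in random order by the existing physicians, masked to patient, visit and histology. Readings are locked before unmasking.
- Live baseline, Day 30 and Month 3 reads used for patient care are recorded separately and are unaffected. The masked read is named as the one used for the imaging outcome, and discordance with the live read is reported.
- The plan states that masking is partial, because of scarring, the earlier punch in preliminary-study patients, and readers recognising lesions.

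The cost is the re-coding work, a second reading of the images, and a delay before final image reads are available. No extra reader, scan or visit is needed.

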6.1 Primary Outcome

Tolerability measured as:

I) Local Skin Reactions (LSRs)

Non-blinded, clinical evaluation of erythema, edema, flaking, crusting/scabbing and pustulation in treated areas will be performed by a physician using a FDA-approved 0-4 point LSR scale at Days 1, 5, 14 and 30 after AFL exposure (Appendix 1). Standardized,

clinical photographs are taken to document LSRs at each visit.

II) Side Effects

Non-blinded, clinical evaluation of prolonged erythema or edema, hyper- or hypopigmentation, scarring and infection will be evaluated up to 3 months after initial AFL treatment.

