3.3 Intervention Summary

For a detailed description of interventions, please see Section 5.

Patients will receive AFL-assisted cisplatin+5-FU as a treatment for their BCC. In brief, treatment areas consisting of tumors and a 5 mm margin will undergo AFL exposure (Ultrapulse DeepFx CO₂ laser, Lumenis, Santa Clara, CA, USA) followed by 60 min topical application of a marketed and commercially available IV cisplatin solution (0.1% Accord Healthcare Limited A/S) at a dose of 0.25 ml per cm². After removal of cisplatin, a commercially distributed 5-FU cream (5% Efudix®, Meda Pharmaceuticals A/S) will be applied to the treatment area at a dose of 0.125 ml per cm² and left under occlusion. After skin evaluations on Day 1 and 5 after treatment, the same 5-FU dose will be applied, again left under occlusion. In total, 5-FU will remain on the skin for 7 days after AFL treatment whereafter it will be washed off.

An additional repeat AFL-cisplatin+5-FU treatment on Day 30 will be offered if tumors persist, based on clinical evaluation and imaging on Day 30.

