3.4 Study Duration and Schedule

Patients will partake in 7 visits over a 3 month period at the dermatological department of Bispebjerg Hospital (time schedule in Section 5):

- 1 Screening visit
- 1 Treatment day
- 5 Control visits after treatment on Day 1, 5, 14, 30 and Month 3

The study is expected to run between March 2018 - March 2019

Recruitment start	1. March 2018
Treatment start	1. March 2018
Final patient treatment	1. December 2018
Final control visit	1. March 2019

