7.4 Punch Biopsy and Blood Sampling

Prior to 4 mm biopsy local analgesic will be used to reduce pain. The biopsy may leave a punctiform scar. Needle-pricks associated with injection and blood sampling (preliminary study) are associated with discomfort. The risk of infection is low (<1%), and will be managed with antibiotics provided by the investigator.

8. Safety Considerations

Patients are followed closely in the initial 30 days after treatment and particularly in the first 14 days. Complete tumor removal is ensured through histological analysis at Month 3. In the event of inadequate treatment response at 3 months, or in the event of withdrawal, patients will receive conventional BCC treatment and follow-up according to national guidelines.

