9.1 Sample size

The primary objective of this explorative trial is to investigate tolerability of AFL-assisted cisplatin+5-FU to ensure that intolerable/severe or serious related adverse events remain minimal for the observed efficacy. While no formal statistical calculation has been performed, 12 superficial and 12 nodular BCCs in 24 subjects are considered sufficient to estimate benefit/risk of the treatment.

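### A repeat course may be given on Day 30, but it has no scheduled local skin reaction score, so in re-treated patients graded tolerability covers one course and Month 3 clearance covers two

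*Combined protocol and SAP*

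**What the plan says.** Section 3.4 (Summary of Outcome Measures and Methods) makes the severity and duration of LSRs over 0-30 days the first part of the primary outcome. Section 6.1 has a physician grade treated areas with a "FDA-approved 0-4 point LSR scale at Days 1, 5, 14 and 30 after AFL exposure". Section 6.3.1 repeats the schedule with a different anchor, "using a FDA-approved LSR scale at Days 1, 5, 14 and 30 after baseline". Appendix 1 gives Days 1-30, and the visit table ticks the scale up to Visit 6 (Day 30).

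Section 3.4 (Study Duration and Schedule) lists "5 Control visits after treatment on Day 1, 5, 14, 30 and Month 3".

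Section 3.3 describes one course: laser and cisplatin on Day 0, then 5-FU under occlusion. It adds: "After skin evaluations on Day 1 and 5 after treatment, the same 5-FU dose will be applied, again left under occlusion". It then states: "An additional repeat AFL-cisplatin+5-FU treatment on Day 30 will be offered if tumors persist". The visit table agrees, with laser, cisplatin and 5-FU in brackets at Visit 6 and a pregnancy test ticked there. On compliance, section 5.4 says: "Securing adequate 5-FU occlusion will occur on control visits".

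Two other statements bear on the point. Section 8 says: "Patients are followed closely in the initial 30 days after treatment and particularly in the first 14 days". Section 9.1 makes no formal calculation but holds that 24 subjects are "considered sufficient to estimate benefit/risk of the treatment".

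**The concern.** The plan foresees a second full course but not the grading of its reactions. If the scoring days run from baseline and no visit lies between Day 30 and Month 3, a patient treated again on Day 30 has no scheduled attendance at which second-course LSRs are graded.

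Tolerability is the primary objective, and section 11 says the combination has not been tried in patients before. A second exposure on recently treated skin is a setting in which tolerability needs to be observed. In a re-treated patient the benefit side (clearance at Month 3) would come from two courses and the graded risk side from one. A summary pooling these patients with those treated once would set two-course efficacy beside one-course LSRs. Section 4 also lets severe LSRs cut recruitment short, and second-course reactions would supply no scheduled grade to that decision.

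**Working it through.** No power or sample-size figure is involved. The check sets the schedule against the treatment plan.

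**Inputs.** From the visit table: Visit 4 = Day 5 ± 2, Visit 5 = Day 14 ± 3, Visit 6 = Day 30 ± 5, Visit 7 = Month 3 ± 5. Sections 6.1 and 6.2 count Month 3 from the first treatment. Assumptions: Month 3 is Day 90 to 92, and a repeat course is given at Visit 6 itself.

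**Step 1: visit ranges.**
- Visit 5: 14 − 3 = 11 to 14 + 3 = 17.
- Visit 6: 30 − 5 = 25 to 30 + 5 = 35.
- Visit 7: 90 − 5 = 85 to 92 + 5 = 97.

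**Step 2: scheduled LSR scores after each course.**

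| | First course | Repeat course |
|---|---|---|
| Nominal scores within 30 days | 4 (Days 1, 5, 14, 30) | 0 |
| Of these, within 14 days | 3 (Days 1, 5, 14) | 0 |

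These counts use nominal days. Visit 5 can fall as late as Day 17 and Visit 6 as late as Day 35, so an individual first course may have only 3 scores within 30 days and 2 within 14. The zeros do not change. The Day 30 score falls at the same visit as the repeat treatment, and no order is stated.

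**Step 3: time from a repeat course to the next listed visit.** Shortest: 85 − 35 = 50 days. Longest: 97 − 25 = 72 days. Section 7.2 expects local effects to resolve within about 30 days, so Month 3 comes 50 − 30 = 20 to 72 − 30 = 42 days after that period. Even a score taken then could show only persistence, not peak severity.

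**Step 4: attendances that a true repeat implies.** 5-FU is reapplied 1 and 5 days after treatment (sections 3.3 and 5.2.4). For a repeat on Day 30 these are Day 30 + 1 = 31 and 30 + 5 = 35. Neither is listed, and nothing says the LSR scale is used at them.

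**Step 5: what scoring those attendances achieves.** The repeat course goes from 0 to 2 scores. If the Day 5 ± 2 window carries over, the last of them falls 3 to 7 days after the repeat. The gap to Month 3 is then 50 − 7 = 43 to 72 − 3 = 69 days, so a sign still present at that score and gone by Month 3 has an end date bracketed only that widely. Early severity is captured; duration is not.

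**The case against.** The strongest reply is that the scoring days can be read per course. Section 6.1 counts from laser exposure and section 3.4 from treatment, and a repeat treatment naturally brings its Day 1 and Day 5 skin evaluations with it. Re-treated patients would then be examined. This stands in part: a reader might infer that nobody looks at the skin after a second course, and the documents do not support that. What is missing is listed visits and a statement that the scale is used. Section 6.3.1 points to baseline as the anchor, and no schedule follows from the per-course reading.

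It also stands that repeat treatment is optional and conditional. The footnote to the visit table requires residual tumour and no crusting, so patients with crusting at Day 30 would not be re-treated then. Prolonged erythema or oedema, pigment change, scarring and infection are followed to Month 3 for everyone, including after a second course.

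A reader might further infer that ending LSR scores at Day 30 is itself an error, because flaking, crusting or pustulation present then gets no later grade. The documents do not support that either. The outcome is deliberately defined over 0-30 days, and unresolved at Day 30 is a complete result for it. Nor would later healing go unseen. Photographs are planned at each visit, and there is clinical assessment at Month 3. Section 8.2 keeps scale LSRs out of AE reporting but does not mention adverse reactions in that exclusion; these are followed until resolved, and whether that route covers persisting LSRs is not stated. The visit table's blank Month 3 cells prove little, since they also omit imaging that section 6.3.2 requires.

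**Conclusion.** The point holds for the repeat course. As written, a second course has 0 scheduled LSR scores against a nominal 4 for the first, and the next listed visit is 50 to 72 days later. The follow-up promised in section 8 is delivered by the listed visits for the first course only, and the benefit/risk estimate of section 9.1 mixes two-course clearance with one-course LSR grades in re-treated patients.

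This rests on section 6.3.1 setting the anchor, on Month 3 being Day 90 to 92, and on the repeat being given at Visit 6. The number of patients affected cannot be derived, because no re-treatment rate is given; it could be anywhere from none to all 24. Patients treated once lose nothing on this point. It is a gap in the schedule and the reporting, worth closing because closing it costs little. It does not invalidate the primary outcome for the first course.

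**What to change.** 1. State that the Day 30 LSR score is taken before any repeat laser exposure.
2. For re-treated patients, list the attendances 1 and 5 days after the repeat (nominally Days 31 and 35) and score the LSR scale at both.
3. Report re-treated patients separately, and state that the graded LSR outcome through Day 30 describes the first course.
4. As a minor addition, score the scale at the existing Month 3 visit, before the biopsy, as a supplementary result. Signs present at Day 30 and gone by Month 3 are then reported as ending between those visits.

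Items 1 to 3 need edits to section 3.4 (Study Duration and Schedule), 6.1, 6.3.1, 9.3 and the visit table. Item 4 also touches section 3.4 (Summary of Outcome Measures and Methods) and Appendix 1.

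Cost: with r patients re-treated out of at most 24, items 1 to 3 add 2r scores, from 0 to 2 × 24 = 48. Item 4 adds up to 24, giving a total of 24 + 2r, or 24 to 72, at perhaps a minute each (an assumption). No attendance is added beyond those a true repeat already implies. Reported reactions may look longer. Second-course reactions around its own Days 14 and 30 stay ungraded, and their duration stays coarsely bracketed; closing that gap would take extra visits.
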